4.3.2.2 Safety Endpoints

The observational endpoints for the evaluation of safety are:

- 1) Occurrence, nature (Medical Dictionary for Regulatory Activities [MedDRA] preferred term), duration, intensity, and relationship to vaccination, and whether the event led to early termination from the study, of any unsolicited systemic AEs reported in the 30 minutes after vaccination(s)

- 2) Occurrence, time of onset, number of days of occurrence, intensity, action taken, and whether the reaction led to early termination from the study, of solicited (prelisted in the subject's diary card and CRB) injection site reactions occurring up to D07 after vaccination(s)
- 3) Occurrence, time of onset, number of days of occurrence, intensity, action taken, and whether the reaction led to early termination from the study, of solicited (prelisted in the subject's diary card and CRB) systemic reactions occurring up to D07 after vaccination(s)
- 4) Occurrence, nature (MedDRA preferred term), time of onset, duration, intensity, action taken, relationship to vaccination (for systemic AEs only), and whether the event led to early termination from the study, of unsolicited AEs up to D30 after vaccination(s)
- 5) Occurrence, nature (MedDRA preferred term), time of onset, duration, seriousness criteria, relationship to vaccination, outcome, and whether the event led to early termination from the study, of SAEs (including AESIs) after vaccination(s) from D0 through the end of the trial
- 6) Occurrence, nature (MedDRA preferred term), time of onset, duration, seriousness criteria, relationship to vaccination, outcome for MAAEs from D30 visit to the 6-month follow-up contact. MAAEs will be collected as unsolicited AEs up to the D30 (+ 14 days) visit

4.3.2.3 Safety Assessment Methods

At the D30 visit, the Investigator or a delegate will ask the subjects or the subjects' parent / guardian about any solicited reactions and unsolicited AEs recorded in the diary card, as well as about any other AEs that may have occurred since the previous visit. All relevant data will be transcribed into the CRB according to the instructions provided by the Sponsor.

4.3.2.3.1 Immediate Post-vaccination Observation Period

Subjects will be kept under observation for 30 minutes after vaccination to ensure their safety. The post-vaccination surveillance should be documented in the source document. Any AE that occurs during this period will be noted on the source document and recorded in the CRB, as follows:

- Unsolicited systemic AEs will be recorded as immediate AEs in the CRB (presence marked as "yes" and details collected)
- Solicited and unsolicited injection site reactions and solicited systemic reactions will be recorded in the CRB in the same way as any reactions starting on the day of vaccination
- SAEs will be recorded in the CRB and reported to the Sponsor in the same way as any other SAEs, according to the procedures described in the protocol

4.3.2.3.2 Reactogenicity (Solicited Reactions from Day 0 to Day 7 after Vaccinations)

After vaccination, subjects or the subjects' parent / guardian will be provided with a diary card, a digital thermometer, and a flexible ruler, and will be instructed how to use them. The following items will be recorded by the subjects or the subjects' parent / guardian in the diary card on the day of vaccination and for the next 7 days (ie, Day 0 through Day 7) until resolution:

- Daily temperature, with the route by which it was taken

- Daily measurement or intensity grade of all other solicited injection site and systemic reactions
- Action taken for each event (eg, medication)

The action(s) taken by the subjects or subjects' parent / guardian to treat and / or manage any **solicited reactions** will be classified in the CRB using the following list (all applicable items should be checked):

- None
- Medication
- Health care provider contact
- Hospitalized
- Discontinuation of study vaccination

Subjects or the subjects' parent / guardian will be contacted by telephone 8 days after vaccination to remind them to record all safety information in the diary card.

If the timing of the telephone call should fall on a weekend or a holiday, the call should be made on the next business day. If contact is not made on the designated day, study staff will continue calling until contact is made. Every telephone attempt and its outcome will be documented in the source document.

[Table 4.1](#) and [Table 4.2](#) present, respectively, the injection site reactions and systemic reactions that are prelisted in the diary cards and CRB, together with the intensity scales.

Table 4.1: Solicited injection site reactions: terminology, definitions, and intensity scales

CRB term (MedDRA lowest level term [LLT])	Injection site pain	Injection site erythema	Injection site swelling
Diary card term	Pain	Redness	Swelling
Definition	Pain either present spontaneously or when the injection site is touched or injected limb is mobilized	Presence of a redness including the approximate point of needle entry	Swelling at or near the injection site Swelling or edema is caused by a fluid infiltration in tissue or cavity and, depending on the space available for the fluid to disperse, swelling may be either soft (typically) or firm (less typical) to touch and thus can be best described by looking at the size of the swelling

Intensity scale*	Grade 1: A type of adverse event that is usually transient and may require only minimal treatment or therapeutic intervention. The event does not generally interfere with usual activities of daily living. Grade 2: A type of adverse event that is usually alleviated with additional therapeutic intervention. The event interferes with usual activities of daily living, causing discomfort but poses no significant or permanent risk of harm to the research participant. Grade 3: A type of adverse event that interrupts usual activities of daily living, or significantly affects clinical status, or may require intensive therapeutic intervention.	Grade 1: ≥ 25 to ≤ 50 mm Grade 2: ≥ 51 to ≤ 100 mm Grade 3: > 100 mm	Grade 1: ≥ 25 to ≤ 50 mm Grade 2: ≥ 51 to ≤ 100 mm Grade 3: > 100 mm
-------------------------	---	--	--

* For the subjective reaction of pain, subjects / parents / guardians will record the intensity level (Grade 1, 2, or 3) in the diary card. For the measurable reactions of redness and swelling, they will record just the size of the reaction, and the classification as Grade 1, 2, or 3 will be assigned at the time of the statistical analysis

Table 4.2: Solicited systemic reactions: terminology, definitions, and intensity scales for adolescents or adults (aged ≥ 12 years)

CRB term (MedDRA lowest level term [LLT])	Fever	Headache	Malaise	Myalgia
Diary card term	Temperature	Headache	Feeling unwell	Muscle aches and pains
Definition	Elevation of temperature to $\geq 38.0^{\circ}\text{C}$ ($\geq 100.4^{\circ}\text{F}$)	Pain or discomfort in the head or scalp. Does not include migraine.	General ill feeling. Malaise is a generalized feeling of discomfort, illness, or lack of well-being that can be associated with a disease state. It can be accompanied by a sensation of exhaustion or inadequate energy to accomplish usual activities.	Muscle aches and pains are common and can involve more than one muscle at the same time. Muscle pain can also involve the soft tissues that surround muscles. These structures, which are often referred to as connective tissues, include ligaments, tendons, and fascia (thick bands of tendons). Does not apply to muscle pain at the injection site which should be reported as injection site pain.
Intensity scale*	Grade 1: $\geq 38.0^{\circ}\text{C}$ to $\leq 38.4^{\circ}\text{C}$, or $\geq 100.4^{\circ}\text{F}$ to $\leq 101.1^{\circ}\text{F}$	Grade 1: A type of adverse event that is usually transient and may require only minimal treatment or therapeutic intervention. The event does not generally interfere with usual activities of daily living.	Grade 1: A type of adverse event that is usually transient and may require only minimal treatment or therapeutic intervention. The event does not generally interfere with usual activities of daily living.	Grade 1: A type of adverse event that is usually transient and may require only minimal treatment or therapeutic intervention. The event does not generally interfere with usual activities of daily living.

	Grade 2: $\geq 38.5^{\circ}\text{C}$ to $\leq 38.9^{\circ}\text{C}$, or $\geq 101.2^{\circ}\text{F}$ to $\leq 102.0^{\circ}\text{F}$	Grade 2: A type of adverse event that is usually alleviated with additional therapeutic intervention. The event interferes with usual activities of daily living, causing discomfort but poses no significant or permanent risk of harm to the research participant.	Grade 2: A type of adverse event that is usually alleviated with additional therapeutic intervention. The event interferes with usual activities of daily living, causing discomfort but poses no significant or permanent risk of harm to the research participant.	Grade 2: A type of adverse event that is usually alleviated with additional therapeutic intervention. The event interferes with usual activities of daily living, causing discomfort but poses no significant or permanent risk of harm to the research participant.
	Grade 3: $\geq 39.0^{\circ}\text{C}$ or $\geq 102.1^{\circ}\text{F}$	Grade 3: A type of adverse event that interrupts usual activities of daily living, or significantly affects clinical status, or may require intensive therapeutic intervention.	Grade 3: A type of adverse event that interrupts usual activities of daily living, or significantly affects clinical status, or may require intensive therapeutic intervention.	Grade 3: A type of adverse event that interrupts usual activities of daily living, or significantly affects clinical status, or may require intensive therapeutic intervention.

* For all reactions but fever, subjects or parents / guardians will record the intensity level (Grade 1, 2, or 3) in the diary card. For fever, they will record the body temperature, and the classification as Grade 1, 2, or 3 will be assigned at the time of the statistical analysis based on the unit used to measure the temperature and the intensity scale.

Important Notes for the Accurate Assessment of Temperature:

Subjects or the subjects' parent / guardian are to measure body temperature once per day, preferably always at the same time. The optimal time for measurement is the evening, when body temperature is the highest. Temperature is also to be measured at the time of any apparent fever. The observed daily temperature and the route of measurement are to be recorded in the diary card, and the highest temperature will be recorded by the site in the CRB. The preferred route for this trial is oral. Pre-vaccination temperature is also systematically collected by the Investigator in the source document. Tympanic thermometers must not be used.

4.3.2.3.3 Unsolicited Adverse Events

In addition to recording solicited reactions, subjects or subjects' parent / guardian will be instructed to record any other medical events that may occur. Space will be provided in the diary card for this purpose.

Information on SAEs will be collected and assessed throughout the study, from the time of vaccination until 6 months after the last vaccination. Any SAE occurring at any time during the study will be reported by the Investigator in the CRB according to the completion instructions provided by the Sponsor; this includes checking the "Serious" box on the AE (electronic) case report form (CRF) and completing the appropriate Safety Complementary Information CRFs. All information concerning the SAE is to be reported either as part of the initial reporting or during follow-up reporting if relevant information became available later (eg, outcome, medical history, results of investigations, copy of hospitalization reports. See protocol for further details on SAE reporting.

For each unsolicited AE (whether serious or non-serious), the following information is to be recorded:

- Start and stop dates^a
- Intensity of the event

For measurable unsolicited AEs that are part of the list of solicited reactions, the size of the AE as well as the temperature for fever will be collected and analyzed based on the corresponding scale used for solicited reactions (see [Table 4.1](#) and [Table 4.2](#)).

All other unsolicited AEs will be classified according to the following intensity scale:

- Grade 1: A type of AE that is usually transient and may require only minimal treatment or therapeutic intervention. The event does not generally interfere with usual activities of daily living

^a The stop date of all related AEs will be actively solicited. For other events, the Investigator will provide the stop date when it becomes available. AEs for which no stop date was obtained during the course of the study will be considered as ongoing at the end of the study.

- Grade 2: A type of AE that is usually alleviated with additional therapeutic intervention. The event interferes with usual activities of daily living, causing discomfort but poses no significant or permanent risk of harm to the research participant
- Grade 3: A type of AE that interrupts usual activities of daily living, or significantly affects clinical status, or may require intensive therapeutic intervention
- Whether the AE was related to the investigational product (for unsolicited systemic AEs)

The Investigator will assess the causal relationship between the AE and the investigational product as either “Not related” or “Related”, as described in Section 4.3.2.7.

- Action taken for each AE (eg, medication)

The action(s) taken by the subjects or subjects’ parent / guardian to treat and / or manage any unsolicited AEs will be classified in the CRB using the following list (all applicable items should be checked):

- None
- Medication
- Health care provider contact
- Hospitalized
- Discontinuation of study vaccination
- Whether the AE was serious

For each SAE, the Investigator will complete all seriousness criteria that apply (outcome, elapsed time, and “Relationship to Study Procedures”)

- Whether the AE caused study discontinuation

4.3.2.4 Serious Adverse Events

Information on SAEs will be collected and assessed throughout the trial, from inclusion until 6 months after vaccination.

Any SAE occurring at any time during the trial will be reported by the Investigator through the electronic data capture (EDC) system and according to the completion guidelines provided by the Sponsor. All information concerning the SAE is to be reported, either as part of the initial reporting or during follow-up reporting if relevant information became available later (eg, outcome, medical history, results of investigations, copy of hospitalization reports. The Investigator will assess the causal relationship between the SAE and the investigational product as either “Not related” or “Related”, as described in protocol.

See protocol for further details on SAE reporting.

4.3.2.5 Medically-Attended Adverse Events

MAAE information will be collected throughout the study. MAAEs that occur from D0 to the D30 (+ 14 days) visit will be recorded as unsolicited AEs on the diary card as part of all

unsolicited AEs collected for this post-vaccination period. MAAEs that occur from D30 to D180 (+ 14 days) will be recorded as such in the MA. An MAAE that occurs within the study period but meets the definition of an SAE should be reported only on the SAE Reporting Form, and not on the MAAE page of the CRF.

The Investigator will assess the causal relationship between the MAAE and the investigational or study product as either “Not related” or “Related,” as described in Section 4.3.2.6.

4.3.2.6 Adverse Events of Special Interest

The following AEs will be captured as AESIs throughout the study:

- Generalized seizures (febrile and non-febrile) (7) (8)
- Kawasaki disease (9) (10)
- Guillain-Barré syndrome (11)
- Idiopathic thrombocytopenic purpura (12) (13)

These events have been listed as AESIs on the basis of the feedback received from the European Union regulators for other studies (conducted in younger age groups).

No safety concerns relating to these AESIs have been identified with the use of MenACYW conjugate vaccine in the completed clinical trials. Because of their medical importance and to ensure expedited communication to the Sponsor, these AESIs are to be considered and collected as SAEs and reported to the Sponsor according to the procedure described in protocol. Further instructions on the data collection for these events and the relevant definitions will be provided in the Operating Guidelines.

4.3.2.7 Assessment of Causality

The Investigator will assess the *causal relationship* between each unsolicited systemic AE and vaccination as either **not related** or **related**, based on the following definitions^a:

Not related – The AE is clearly / most probably caused by other etiologies such as an underlying condition, therapeutic intervention, or concomitant therapy; or the delay between vaccination and the onset of the AE is incompatible with a causal relationship; or the AE started before the first vaccination (screening phase, if applicable)

Related – There is a “reasonable possibility” that the AE was caused by the product administered, meaning that there is evidence or arguments to suggest a causal relationship

Note: By convention, all AEs reported at the injection site (whether solicited or unsolicited) and all solicited systemic AEs are considered to be related to the administered product and therefore are referred to as reactions and do not require the Investigator’s opinion on relatedness.

Adverse events likely to be related to the product, whether serious or not, that persist at the end of the study will be followed up by the Investigator until their complete disappearance or the

^a ICH Guidelines, Clinical Safety Data Management E2A

stabilization of the subject's condition. The Investigator will inform the Sponsor of the date of final disappearance of the event or the date of "chronicity" establishment.

4.4 Derived Endpoints: Calculation Methods

4.4.1 Immunogenicity

4.4.1.1 Computed Values for Analysis

In order to appropriately manage extreme values (< LLOQ and \geq upper limit of quantitation [ULOQ]) for analysis purposes, the following computational rule is applied to the values provided in the clinical database for each blood sample drawn:

- If a value is < LLOQ, then use the computed value LLOQ/2
- If a value is between \geq LLOQ and < ULOQ, then use the value
- If a value is \geq ULOQ, then use the computed value ULOQ

4.4.1.2 Seroprotection

hSBA vaccine seroprotection for serogroups A, C, Y, and W is defined as hSBA titer $\geq 1:8$.

4.4.1.3 Fold-Rise

The derived endpoint fold-rise is driven by both baseline and post-baseline computed values and is computed as follows. Generally, for extreme values, this algorithm minimizes the numerator and maximizes the denominator.

- If the baseline computed value is < LLOQ and the post-baseline computed value is < LLOQ, then the fold-rise is 1
- If the baseline computed value is \geq LLOQ and the post-baseline computed value is \geq LLOQ, then the fold-rise is post-baseline computed value / baseline computed value
- If the baseline computed value is \geq LLOQ and the post-baseline computed value is < LLOQ, then the fold-rise is (LLOQ/2) / baseline computed value
- If the baseline computed value is < LLOQ and the post-baseline computed value is \geq LLOQ, then the fold-rise is post-baseline computed value / LLOQ

If the computed value is ≥ 4 , then the derived ≥ 4 -fold rises indicator will be "Yes" for that test, otherwise ≥ 4 -fold rises will be "No".

Note: If baseline or post-baseline is missing, then fold-rise is missing.

4.4.1.4 A, C, Y, W Seroresponse

hSBA vaccine seroresponse for serogroups A, C, Y, and W is defined as follows:

- For a subject with a pre-vaccination titer $< 1:8$, the post-vaccination titer must be $\geq 1:16$
- For a subject with a pre-vaccination titer $\geq 1:8$, the post-vaccination titer must be at least 4- fold greater than the pre-vaccination titer

rSBA vaccine seroresponse for serogroups A, C, Y, and W is defined as follows:

- A post-vaccination rSBA titer $\geq 1:32$ for subjects with pre-vaccination rSBA titer $< 1:8$
- A post-vaccination titer ≥ 4 times the pre-vaccination titer for subjects with pre-vaccination rSBA titer $\geq 1:8$

4.4.2 Safety

4.4.2.1 Solicited Reactions

4.4.2.1.1 Daily Intensity

All daily records for solicited reactions will be derived into daily intensity according to the following classification: None, Grade 1, Grade 2, Grade 3, or Missing.

For the derivation of daily intensities, the following sequential steps will be applied:

- 1) Solicited reactions (except Fever/Pyrexia) with an Investigator presence recorded as "No" and with all daily records missing, then all daily intensities will be derived as None
- 2) For a temperature partially missing after decimal point, the data will be analyzed replacing "MD" (missing data) by zero. For example, a "39.MD" daily temperature will be considered as "39.0°C" at the time of analysis.
- 3) For non-measurable (NM) solicited reactions, daily intensities will correspond to daily records reported in the clinical database. For measurable solicited reactions the daily measurements reported in the clinical database will be converted based upon the intensity scales defined in the protocol; this assumes a reaction that is too large to measure (NM) is Grade 3.

Note: The maximum intensity on the ongoing period is derived from the record of the maximum intensity / measurement after the end of the solicited period following the rule described above.

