13.2 Source Data and Source Documents

“Source data” are the data contained in source documents. Source documents are original documents or certified copies, and include, but are not limited to diary cards, medical and hospital records, screening logs, informed consent / assent forms, telephone contact logs, and worksheets. The purpose of study source documents is to document the existence of subjects and to substantiate the integrity of the study data collected. Investigators must maintain source documents so that they are accurate, complete, legible, and up to date.

For missing or discrepant data on a diary card, the study coordinator will obtain verbal clarification from the subject, enter the response into the “Investigator’s comment” page of the diary card, and transfer the information to the CRB.

The subject pre-screening log should list all individuals contacted by the Investigators to participate in the trial, regardless of the outcome.

The Investigator must print^a any electronic records on an ongoing basis, sign and date them immediately after creation, and keep the printouts on file as source documents that can be verified by the Sponsor or an inspector against the electronic records. Any subsequent changes of an electronic record require the record to be re-printed, dated (with an indication of the date of change), and signed. Such records must also be kept together with the original printed copy.

Good Documentation Practice should be followed by the Investigator and the site staff managing source documents.

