4.4.2.1.3 Presence

Presence is derived from the maximum overall intensity on the period considered:

- None: No presence
- Grade 1, Grade 2, or Grade 3: Presence

- Missing: Missing presence

Subjects with at least 1 non-missing presence (maximum overall intensity ≥ 0) for a specific endpoint will be included in the analysis. Conversely, those without a non-missing presence will not be included in the analysis of the endpoint.

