5.3.1.4 Intensity

For solicited reactions, missing intensities will be handled as described in Section 4.4.2.1.1. For unsolicited non-serious AEs, missing intensities will remain missing and will not be imputed.

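### SAP 4.4.2.1.1 accepts an Investigator 'No' when diary records are missing but has no rule for a 'Yes', so rates of pain, headache, malaise and myalgia can be understated

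*SAP*

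**What the plan says.** SAP 4.4.2.1.1 derives daily intensities in sequential steps. Step 1 leaves fever aside and applies to all other solicited reactions: where the Investigator's entry is No "and with all daily records missing, then all daily intensities will be derived as None". Step 2 deals with partly recorded temperatures. Step 3 works from the diary: for reactions that are not measured, "daily intensities will correspond to daily records reported in the clinical database", and for measured ones the recorded size is converted to a grade.

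SAP 4.4.2.1.3 then states that "Presence is derived from the maximum overall intensity on the period considered". If that maximum is missing, the result is "Missing: Missing presence", and "those without a non-missing presence will not be included in the analysis of the endpoint".

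No other section fills the gap. SAP 5.3.1.4 points back: "For solicited reactions, missing intensities will be handled as described in Section 4.4.2.1.1". SAP 5.3.1 says that missing safety data are not replaced.

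**The concern.** With no daily records, the same field is believed when it denies a reaction and has no effect when it confirms one. Deniers enter the denominator as non-events; confirmers leave both numerator and denominator. Fever does not have this problem, because step 1 excludes it and neither answer is used.

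The SAP elsewhere resolves missing safety data cautiously: missing causality becomes Related (4.4.2.5.5), and unsolicited events with missing onset stay in the analysis (4.4.2.2.4). Step 1 without a counterpart leans the other way.

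The case can occur. Investigator assessment of solicited reactions is mandatory (SAP 4.3.2.1), Protocol 5.1.4 foresees diary cards that are not returned, and step 1 itself presupposes presence answers without daily records.

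At stake are solicited injection site and systemic reactions, safety endpoints 2 and 3 in SAP 4.3.2.2, reported as percentages with 95% confidence intervals. Groups 1 and 2 have 200 subjects each in order to build the booster safety database (SAP 5.5).

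**Working it through.** The plan states no reactogenicity rate, diary-missingness rate or bias, so there is no figure of its own to reproduce.

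**1. Trace of the rule (non-fever reaction, all daily records missing)**

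| Investigator presence | Daily intensity | Presence | In the endpoint? |
|---|---|---|---|
| No | None on every day (step 1) | No | Yes, as a non-event |
| Yes | Missing (no step applies; step 3 has nothing to convert) | Missing | No, excluded by 4.4.2.1.3 |

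The second row is inferred from the absence of a rule, but it is what the text produces when followed as written.

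**2. Direction**

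Let D be the number of subjects with diary data, p the reaction rate among them, and m_no and m_yes the numbers without diary data whose Investigator answer is No or Yes.

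- SAP rate: r = pD / (D + m_no)
- Rate using both answers: R = (pD + m_yes) / (D + m_no + m_yes)
- Difference: R − r = (1 − r) × m_yes / (D + m_no + m_yes)

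The difference is never negative, is zero when m_yes = 0, and is positive when m_yes > 0 and r < 100%. So r cannot lie above R.

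**3. Size**

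Assume a share f of the group lacks diary data and reacts at the same rate p. Per subject enrolled, D = 1 − f, m_no = f(1 − p) and m_yes = fp. Then R = p and r = p(1 − f) / (1 − fp).

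Example with p = 45% and f = 5%: r = 0.45 × 0.95 / (1 − 0.0225) = 0.4275 / 0.9775 = 43.73%, so r − R = −1.27 points.

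r − R in percentage points:

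| f | p = 5% | p = 20% | p = 45% |
|---|---|---|---|
| 2% | −0.10 | −0.32 | −0.50 |
| 5% | −0.24 | −0.81 | −1.27 |
| 10% | −0.48 | −1.63 | −2.59 |

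Bounds on the answers given by subjects without diary data:

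- All No: r = R, so the difference is 0.
- All Yes: r = p and R = p(1 − f) + f, so r − R = −f(1 − p). At f = 5% this is −4.75, −4.00 and −2.75 points for p = 5%, 20% and 45%; at f = 10% it is −9.50, −8.00 and −5.50.

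None of these differences depends on group size.

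**4. Redness and swelling**

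Grades come from the recorded size, and Grade 1 starts at 25 mm (SAP Table 4.1). A Yes without a size may be below 25 mm and so not an event. If all such subjects were below 25 mm, the true rate would be pD / (D + m_no + m_yes), which is smaller than r when m_yes > 0: excluding them would raise the reported rate. Step 2 above therefore fixes the direction against the Investigator's answers, but not against the truth, for these two reactions.

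**The case against.** Several objections have force.

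- **The cell may be empty.** Under Protocol 13.2, for missing or discrepant diary data, "the study coordinator will obtain verbal clarification from the subject", and the answer goes into the case report book. Outstanding diary information is collected at the D30 visit (Protocol 5.1.4), and consistency checks follow (Protocol 11.2). These steps shrink the Yes-without-records cell, but nothing guarantees that daily grades are recovered.
- **The effect is small.** At p = 45%, the shift of 0.5 to 1.3 points compares with an approximate 95% half-width of 1.96 × √(0.45 × 0.55 / 200) = 6.9 points at n = 200 and 9.8 at n = 100. Safety is descriptive and the same rule applies in all four groups. This stands, and no hypothesis test or sample size is affected.
- **Measurement should outrank a flag.** SAP 4.4.2.1.7 sets aside the Investigator's ongoing flag in favour of the measurement. This stands against overriding diary values that were recorded, for example when every recorded day is below Grade 1. It says less where there is no record at all, and step 1 already uses a flag there.
- **Step 1 may be deliberate.** A form on which No leaves the daily grid blank would need it (an inference; the form is not in the documents). Deleting it could then exclude true non-reactors. If half of the No subjects had blank grids at p = 45%, the rate would become 0.45 / (0.45 + 0.275) = 62%. This stands against deletion.

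A reader might infer that every non-fever rate is biased downward. The documents do not support that: bias needs at least one Yes-without-records subject for that reaction and group, and no count is given.

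**Conclusion.** The asymmetry is in the SAP text, and followed as written it removes confirmed reactors while keeping denied ones. For pain, headache, malaise and myalgia, the percentage with any reaction can be understated, never overstated, relative to using both Investigator answers. The bias is zero where no such subject exists and about 0.1 to 1.3 points under the assumptions that 2% to 5% of subjects lack diary data, that they react at the same rate as the others, and that the rate lies between 5% and 45%.

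Two stronger readings should not be drawn. Calling the bias downward against the truth for all six non-fever reactions fails for redness and swelling because of the 25 mm threshold. Nor is step 1 wrong in itself: it uses a recorded answer, and what is missing is its counterpart. This is a modest gap in the derivation rules, worth closing because otherwise confirmed reactions drop out of the rates.

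**What to change.** Keep step 1 and add its counterpart to SAP 4.4.2.1.1 and 4.4.2.1.3:

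- **Pain, headache, malaise and myalgia:** if Investigator presence is Yes and all daily records are missing, derive presence as Yes with maximum intensity Missing. Count the subject in the numerator and denominator of the 'any' row only.
- **Redness and swelling:** keep intensity Missing, report the number of such subjects by group, and add a sensitivity row that counts them as events.
- **Recorded values:** do not override daily values that are present and all below Grade 1.

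The cost is a short addition to the SAP, a few lines of derivation code and one extra row for each of the two measured reactions. The downside is that the grade rows may not sum to the 'any' row, which a table footnote can explain.
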